Application of Economics & Social psychology to improve Opioid Prescribing Safety (AESOPS) Trial 2 is a multi-site randomized trial that takes place among a clinic organization in Los Angeles, California (AltaMed Health Services) and one in Chicago, Illinois (Northwestern University). Participants in the trial are clinicians. Observations are visits where opioids are prescribed. Clinicians are randomized to receive either: 1) guidelines on opioid prescribing, or 2) information on an opioid harm experienced by one of their patients (non-fatal or fatal overdose). In Los Angeles, fatal overdose letters are already required by the County, therefore, only non-fatal overdose letters will be sent to clinicians in Los Angeles. These will be signed by the County Public Health Officer. In Chicago, Illinois, both types of letters will be sent. Outcomes are milligram morphine equivalents ordered by each participating clinician per week. A secondary outcome is referrals to medication assisted treatment. These data are collected from the electronic health record systems at AltaMed and Northwestern Medical Center. Determining overdoses involves connecting data on overdoses between hospital systems, or in the case of Illinois, state vital records. More specifically, non-fatal overdoses in Los Angeles connect opioid prescribing at AltaMed with Los Angeles County emergency department data (See Appendix 1, Figure 1a), non-fatal overdoses at Chicago's Northwestern University involve a search of the internal database that connects that University's outpatient clinic data with emergency department data (See Appendix 1, Figure 1b), and fatal overdoses among patients at Northwestern connect data from that institution with Illinois State Vital records (Illinois Department of Public Health (IDPH); See Appendix 1, Figure 1c). A pilot study was originally approved for the data exchange in Figure 1c and the secure data sharing exercise was successful.

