The goal of the project is to dampen the intensity and frequency of opioid prescribing and to increase awareness and use of medication assisted therapy for persons with opioid use disorder through a cluster randomized trial. Overdose notification letters (See Appendix 2 and 3) will be sent to primary care clinicians randomized to the experimental study arm and meeting inclusion criteria at AltaMed Health Services or Northwestern Medicine. Both letters will include "if/when/then" language which advises the clinician to keep the letter's recommendations close when their next patient presents with pain. Clinicians notified of their patient's overdose will be compared to a control group receiving guideline education and no notification of their patient's overdose (Appendix 6). To quantify the effect of the notification letter, we will measure the change in clinician weekly milligram morphine equivalent (MME) prescribed to all of their patients in 6-month periods before and after receiving overdose feedback letters. The secondary outcomes include the change in proportion of patients prescribed at least 50 daily MME, buprenorphine referrals for medication assisted therapy, and access rates for referral links included in the letter.

Because the letters include patient identifying information linked to outpatient prescribing records, we requested a HIPAA waiver of authorization to match outpatient records to mortality and non-fatal overdose records. The research could not feasibly be conducted if research participants' authorization were required. AltaMed will release information under the auspices of a waiver of HIPAA authorization. USC and AltaMed have a fully executed Business Associates Agreement, Memorandum of Understanding and Data Use Agreement; Northwestern and IDPH and USC and Northwestern have a fully executed Data Use Agreement. AltaMed and Northwestern will cede to the County IRB as the IRB of record for this study.

To create the list of overdose patients for whom opioids were prescribed, outpatient records will be linked to the emergency department and, in the case of Northwestern patients, IDPH death records. Overdose data will be linked with outpatient records using matching software that complies with institutional security and privacy standards at IDPH and Los Angeles County. Where an existing direct link code is available (e.g. MRN), we will use the code.

Primary hypotheses:

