1. Clinicians randomized to the overdose notification group will exhibit a greater reduction in weekly MME from the pre- to post-period compared to clinicians randomized to the control group for fatal and non-fatal overdoses.
2. Among the clinicians who prescribed at least one opioid in the study period, those randomized to the overdose notification group will exhibit a greater reduction in the proportion of a clinician's patients prescribed at least 50 daily MME from the pre- to post-period compared to clinicians randomized to the control group for fatal and non-fatal overdoses.

b) Number of subjects:

AltaMed Health Services is a private health system in Los Angeles, California. AltaMed has 35 clinics with 134 clinicians with 17,674 such patients. Clinicians meeting inclusion criteria will be enrolled in the study. Northwestern Medicine is a regional health system affiliated with an academic medical center located in the Chicago region of Illinois and includes 60 primary care clinics that contain 387 clinicians with 12,552 patients using chronic opioid therapy for noncancer pain—on opioids for greater than three months.

c) Mechanism for subject selection or exclusion:

Eligible physicians and patients will be identified using outpatient opioid prescribing data

from electronic medical records. A clinician is eligible for inclusion if: 1) s/he prescribed a qualifying scheduled drug to a patient in the 12 months prior to their fatal or non-fatal overdose 2) the patient is 18 years old or older at the time of the overdose, 3) s/he practices within a health system enrolled in the study, and 4) the overdose occurs during the 12-month observation period.

A patient is eligible for identification in a physician notification if s/he (a) has been prescribed an opioid by an eligible clinician (b) has a documented overdose event in EHR or mortality data. Patients without overdose events will be excluded. Patients with fatal overdoses in Los Angeles County will be excluded to avoid redundancy with existing notification practices.

[figure not shown]
d) Duration of intervention:

The duration of the overdose notification intervention is one day.

e) Total duration which study will be performed (data collection, intervention, and analysis period):

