$$(pills)_{ijk}^* = \beta_1 + \beta_2 Time_{ij} + \beta_3 (Time_{ij} - t^*) + \beta_4 Group_i + \beta_5 Overdose Type_k + \beta_6 Group_i * Overdose Type_k + \beta_7 Time_{ij} * Group_i + \beta_8 (Time_{ij} - t^*) * Group_i + \beta_9 Time_{ij} * Overdose Type_k + \beta_{10} (Time_{ij} - t^*) * Overdose Type_k + \beta_{11} Time_{ij} * Group_i * Overdose Type_k + \beta_{12} (Time_{ij} - t^*) * Group_i * Overdose Type_k + \eta + \delta_{i(k)} + error$$

where $(pills)_{ijk}^*$ denotes the dependent variable for clinician i in week j , $Time_{ij}$ is the study week indexed by j , t^* is the spline knot for the start of the intervention, $(Time_{ij} - t^*)$ is a truncated line function that is equal to $(Time_{ij} - t^*)$ when $Time_{ij} > t^*$ and 0 otherwise to allow for nonlinear trends in prescribing following the intervention, $Group_i$ is dichotomous for the overdose notification intervention group, $Overdose Type_k$ is dichotomous for a fatal overdose, η is the clinic random effect, and $\delta_{i(k)}$ is the random effect for each clinician i who prescribed to patient k who suffered an overdose.

The mixed logistic regression model for our secondary outcomes is shown in Eq. 2:

$$(high dose Rx)_{ijk} = \beta_1 + \beta_2 Time_{ij} + \beta_3 Group_i + \beta_4 Overdose Type_k + \beta_5 Group_i * Overdose Type_k + \beta_6 Time_{ij} * Group_i + \beta_7 Time_{ij} * Overdose Type_k + \beta_8 Time_{ij} * Group_i * Overdose Type_k + \eta + \delta_{i(k)} + error$$

where $(high\ dose\ Rx)_{ijk}$ is whether the visit had a high dose prescription of 50 MME or greater (yes vs. no) for clinician i , $Time_{ij}$ is the study period (pre- vs. post-intervention) indexed by j , $Group_i$ is dichotomous for the overdose notification intervention group, $Overdose\ Type_k$ is dichotomous for a fatal overdose, η is the clinic random effect, and $\delta_{i(k)}$ is the random effect for each clinician i who prescribed to patient k who suffered an overdose. We will compute the estimated pre- to post-intervention change in the mean proportion of high dose patient visits for each of the four intervention groups: nonfatal control, nonfatal letter, fatal control, fatal letter. The proportion will be calculated by dividing the total number of patient visits where an opioid of at least 50 MME was prescribed by the total number of opioid prescriptions.

E. Privacy of Individuals and Confidentiality of Data

We will utilize two types of data for this study:

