When your next patient presents with pain, keep the above 6 recommendations close at hand to assist with their safe care. Also, be comfortable voicing your concern about prescribing safety with them so that they are also aware of the dangers associated with scheduled drugs. We also encourage you to routinely log into ILPMP and learn more about the prescriptions your patient received leading up to the overdose.

This letter is meant to be informative only and there is no expectation of reply. We understand that learning of your patient’s overdose can be difficult. We hope that you will join us in our effort to prevent future drug overdoses. Please take this as an opportunity to talk with your patient and perhaps other patients in your practice who may be at-risk.

Sincerely,

[Medical Director or similar role]

ⁱ Lev, R., Petro, S., Lee, O., Lucas, J., Stuck, A., Vilke, G. M., & Castillo, E. M. (2016). A description of Medical Examiner prescription-related deaths and prescription drug monitoring program data. *The American journal of emergency medicine*, 34(3), 510–514.
<https://doi.org/10.1016/j.ajem.2015.12.023>

PRESCRIBING OPIOIDS FOR CHRONIC PAIN

ADAPTED FROM CDC GUIDELINE

Opioids can provide short-term benefits for moderate to severe pain. Scientific evidence is lacking for the benefits to treat chronic pain.

IN GENERAL, DO NOT PRESCRIBE OPIOIDS AS THE FIRST-LINE TREATMENT FOR CHRONIC PAIN (for adults 18+ with chronic pain > 3 months excluding active cancer, palliative, or end-of-life care).

BEFORE PRESCRIBING

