3 TALK TO PATIENTS ABOUT TREATMENT PLAN

- Set realistic goals for pain and function based on diagnosis.
- Discuss benefits, side effects, and risks (e.g., addiction, overdose).
- Set criteria for stopping or continuing opioid. Set criteria for regular progress assessment.
- Check patient understanding about treatment plan.

4 EVALUATE RISK OF HARM OR MISUSE. CHECK:

- Known risk factors: illegal drug use; prescription drug use for nonmedical reasons; history of substance use disorder or overdose; mental health conditions; sleep-disordered breathing.
- Prescription drug monitoring program data (if available) for opioids or benzodiazepines from other sources.
- Urine drug screen to confirm presence of prescribed substances and for undisclosed prescription drug or illicit substance use.
- Medication interactions. AVOID CONCURRENT OPIOID AND BENZODIAZEPINE USE WHENEVER POSSIBLE.

WHEN YOU PRESCRIBE

START LOW AND GO SLOW. IN GENERAL:

- Start with immediate-release (IR) opioids at the lowest dose for the shortest therapeutic duration. IR opioids are recommended over ER/LA products when starting opioids.
- Avoid ≥ 90 MME/day; consider specialist to support management of higher doses.
- If prescribing ≥ 50 MME/day, increase follow-up frequency; consider offering naloxone for overdose risk.
- For acute pain: prescribe < 3 day supply; more than 7 days will rarely be required.
- Counsel patients about safe storage and disposal of unused opioids.

See below for MME comparisons. For MME conversion factors and calculator, go to TurnTheTideRx.org/treatment.

50 MORPHINE MILLIGRAM EQUIVALENTS (MME)/DAY:

- 50 mg of hydrocodone (10 tablets of hydrocodone/acetaminophen 5/300)
- 33 mg of oxycodone (~2 tablets of oxycodone sustained-release 15mg)

90 MORPHINE MILLIGRAM EQUIVALENTS (MME)/DAY:

- 90 mg of hydrocodone (18 tablets of hydrocodone/acetaminophen 5/300)
- 60 mg of oxycodone (4 tablets of oxycodone sustained-release 15mg)

AFTER INITIATION OF OPIOID THERAPY

ASSESS, TAILOR & TAPER

- Reassess benefits/risks within 1-4 weeks after initial assessment.
- Assess pain and function and compare results to baseline. Schedule reassessment at regular intervals (≤ 3 months).
- Continue opioids only after confirming clinically meaningful improvements in pain and function without significant risks or harm.
- If over-sedation or overdose risk, then taper. Example taper plan: 10% decrease in original dose per week or month. Consider psychosocial support.

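### Hypothesis 2 is about the share of a clinician's patients at 50 daily MME or more, but the SAP models visits and divides visits by prescriptions, so no planned analysis estimates the hypothesised proportion

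*Combined protocol and SAP*

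**What the plan says.** Section B.a, Primary hypotheses, number 2, is limited to clinicians who prescribed at least one opioid in the study period. It predicts a greater fall in the letter arm in the proportion of a clinician's "patients prescribed at least 50 daily MME from the pre- to post-period". The Study Synopsis in the same section also counts patients, but ranks the outcome differently: "The secondary outcomes include the change in proportion of patients prescribed at least 50 daily MME". The Synopsis also says "Observations are visits where opioids are prescribed".

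Section D introduces Eq. 2 as the mixed logistic model for the secondary outcomes. Its dependent variable is "whether the visit had a high dose prescription of 50 MME or greater". The quantity to be estimated is the pre-to-post change in "the mean proportion of high dose patient visits for each of the four intervention groups". The formula given for that figure is "dividing the total number of patient visits where an opioid of at least 50 MME was prescribed by the total number of opioid prescriptions".

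**The concern.** Three units are in play for one outcome: patients in the hypothesis, visits in the model, and visits over prescriptions in the reported figure. An analyst who follows section D exactly will produce a model estimate and a descriptive proportion that need not agree with each other. Neither answers Hypothesis 2 as worded. The threshold also changes from daily MME to plain MME.

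An outcome listed under the primary hypotheses therefore has no matching analysis. The text also leaves room to choose among three ratios after results are known. A visit measure weights each patient by the number of opioid visits, so it can move when no patient has changed dose group. A patient measure can stay still when prescribing within the period has changed.

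**Working it through.** The plan states no baseline rate, power or effect size for this outcome, so there is no figure to reproduce. The check is a comparison of definitions, followed by arithmetic on assumed caseloads.

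**1. Definitions side by side**

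| Place | Counted | Divided by | Threshold | Status |
|---|---|---|---|---|
| B.a, Hypothesis 2 | patients | the clinician's patients (all or opioid-treated not stated) | 50 daily MME | primary |
| B.a, Study Synopsis | patients | patients (group not stated) | 50 daily MME | secondary |
| D, Eq. 2 | visit, yes/no | visits (opioid visits, on the Synopsis wording) | 50 MME | secondary |
| D, ratio after Eq. 2 | high-dose visits | opioid prescriptions | 50 MME | as Eq. 2 |

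The missing word matters if the text is taken literally. The pocket guide in Appendix 5 equates 50 MME with 10 tablets of hydrocodone/acetaminophen 5/300. If the threshold were applied to a whole prescription, 10 such tablets in total would count as high dose.

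**2. How far the three ratios can differ.** Assume 20 opioid patients: H = 4 high-dose and L = 16 lower-dose. Lower-dose patients have one visit and one prescription each. High-dose patients have v visits each and r prescriptions per visit.

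- Patient share = H/(H + L)
- Visit share = Hv/(Hv + L)
- SAP ratio = Hv/(Hvr + L)

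| v | r | Patient share | Visit share | SAP ratio |
|---|---|---|---|---|
| 1 | 1 | 4/20 = 20% | 4/20 = 20% | 4/20 = 20% |
| 1 | 2 | 20% | 20% | 4/24 = 16.7% |
| 6 | 1 | 20% | 24/40 = 60% | 24/40 = 60% |
| 6 | 2 | 20% | 60% | 24/64 = 37.5% |
| 4 | 2 | 20% | 16/32 = 50% | 16/48 = 33.3% |

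The last two rows can be read as before and after. High-dose visits fall from 6 to 4 per patient and nobody leaves the high-dose group. Both section D measures fall, while the Hypothesis 2 proportion does not move. In the extreme case where every visit is high-dose with two prescriptions, the SAP ratio is 1/2 = 50% and the visit share is 100%. Agreement is guaranteed only with one visit per patient and one prescription per visit. Other caseloads can agree by coincidence, for example if both dose groups average the same number of visits.

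**3. What this could do to the arm comparison.** Assume 10 high-dose and 90 lower-dose patients in each arm throughout, with one visit each at the start. The patient-level odds ratio (letter/control) is then 1.00. Let high-dose visits rise by a net fraction g in one arm only.

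- Rise in control: visit OR = 1/(1 + g) = 0.91, 0.83, 0.77 for g = 0.1, 0.2, 0.3
- Rise in the letter arm: visit OR = 1 + g = 1.10, 1.20, 1.30
- Equal rise in both arms: OR = 1.00

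**4. The reverse case.** Assume 100 opioid patients with 6 visits each, 10 of them high-dose before the letter. Afterwards 5 of the 10 drop below 50 MME after their second visit. High-dose visits go from 10 × 6 = 60 to 5 × 6 + 5 × 2 = 40. The visit share goes from 60/600 = 10.0% to 40/600 = 6.7%, OR (40/560)/(60/540) = 0.64. A patient counted as high-dose if ever so in the period stays high-dose, so the patient share remains 10%.

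**5. The denominator.** Among opioid recipients, suppose the letter arm goes from 10 high-dose and 90 lower-dose patients to 9 and 72, with control unchanged. The share rises from 10.0% to 9/81 = 11.1%, OR (9/72)/(10/90) = 1.13, while the number of high-dose patients falls.

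**The case against.** The best defence is that visits were meant all along. The Synopsis names opioid visits as the observations, and Eq. 2 with its mean visit proportion follows that unit. On this view only the wording of Hypothesis 2 and one word in the ratio are wrong. This is a fair reading, and it means the plan can be repaired in either direction. It does not remove the problem: Hypothesis 2 and the Synopsis still say patients, and visits over prescriptions is not a visit proportion.

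A reader might go further and infer that patients are the only acceptable unit. The documents do not support that. Step 4 shows that an ever-in-period patient measure can miss a gradual reduction within the period, and both letters list tapering among their recommendations.

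A reader might also infer that Eq. 2 is biased toward one arm. The control guide says, for patients at or above the threshold, "50 MME/day, increase follow-up frequency". The nonfatal letter says "Please take this as an opportunity to talk with your patient and perhaps other patients in your practice who may be at-risk". Neither text is about opioid-prescribing visits as such, and the fatal letter carries no such invitation. The percentages in step 3 are assumptions, the net direction is unknown, and equal changes cancel.

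Two further points on the other side stand. If prescriptions per visit are stable across arms and periods, the faulty ratio shifts only the level: at an assumed 1.1 prescriptions per visit, a 10.0% visit share is reported as 10/110 = 9.1%. The intended denominator is probably opioid recipients, given the restriction to opioid prescribers and opioid visits, and a share among recipients is a legitimate measure. Step 5 is therefore a caution on interpretation and a reason to state the group, not a separate error.

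**Conclusion.** The contradiction is in the text and needs no assumption. The patient proportion of Hypothesis 2 is not what Eq. 2 models, the reported ratio matches neither, the threshold loses its daily qualifier, and the outcome is primary in one place and secondary in two. It should be corrected before the outcome is analysed.

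The effect on the arm comparison is not established. In the assumed caseload of step 2, a fixed patient share of 20% goes with visit shares of 20% to 60% and SAP ratios of 16.7% to 60%. These figures show that the measures can separate, not by how much they will in this trial. The documents give no visits per patient or prescriptions per visit. Northwestern's patients are described as on opioids for more than three months, which makes one visit and one prescription each unlikely. Even so, a claim that the result will favour either arm would go beyond the plan. The weekly MME outcome is not touched.

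**What to change.** 1. In section D, replace the visits-over-prescriptions ratio with one whose numerator and denominator share a unit, and write the threshold as daily MME throughout.
2. Use the same unit in Hypothesis 2, the Study Synopsis and Eq. 2, by one of two routes:
   - *Patient level.* Analyse one record per patient per period, with opioid recipients as the stated denominator. Give a rule for a single daily-MME value per patient per period that is not simply ever-in-period. Report high-dose opioid visits over opioid visits alongside.
   - *Visit level.* Keep Eq. 2 and reword Hypothesis 2 and the Synopsis to the share of opioid visits that are high-dose.
3. Report numerator and denominator counts by arm and period next to every proportion.
4. Give the outcome the same status, primary or secondary, in the hypotheses, the Synopsis and section D.

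A patient random effect and a patient panel fixed before the letter are optional extras and not part of this correction.

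The visit-level route costs rewording only. The patient-level route adds a little re-aggregation, and section B.f already assigns each patient a study identifier. One limitation remains under both routes: a share among opioid recipients or opioid visits moves with its denominator, so it must be read with the counts.

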Appendix 1. Figures 1a-1c

Figure 1a. Schematic view of study procedures for communicating non-fatal overdose in Los Angeles. (Fatal overdose letters are mandated by Los Angeles County and are not part of the study).

[figure not shown]

Figure 1b. Schematic view of study procedures for communicating non-fatal overdose in Chicago, Illinois.

[figure not shown]
[figure not shown]

Figure 1c. Schematic view of study procedures for communicating fatal overdose in Chicago, Illinois. A pilot project has already been completed.

Appendix 2. Fatal Overdose Notification Letter to Clinician

Dear *(Name of Prescriber)*,

This letter is to inform you that your patient, {Name, Date of Birth}, died on {Date}. Prescription opioid overdose was either the primary cause of death or contributed to the death.

Northwestern Medicine is tracking outcomes for patients on opioids and other scheduled drugs.

A significant proportion of overdoses are due to the combination of opioids with a sedative medication. Patients may obtain legitimate prescriptions for opioids, benzodiazepines, muscle relaxants, and sleep aids from more than one prescriber. When taken in any combination, these medications put patients at greater risk of overdose and death. Many fatal and non-fatal overdoses are a result of long-term therapeutic prescribing or of combined prescription medications with drugs obtained from other sources.

Our aim is to alert clinicians to the potential dangers of opioid medications and how common death from misuse of these medications is in Chicago and throughout Illinois.

Northwestern Medical Group would like to remind you that Illinois has a prescription drug monitoring program called the Illinois Prescription Monitoring Program (ILPMP) which *helps prescribers avoid prescribing controlled substances when they are likely to do more harm than good*.

ILPMP contains information about whether and when other clinicians have prescribed controlled substances to your patient within the last 12 months. With few exceptions, prescribers are required by state law to check the ILPMP when prescribing opioids. **Review of the ILPMP could alert you to problematic medication usage, potential addiction or diversion, and help inform safe medication prescribing and monitoring.**

This information is available through Epic and at <https://www.ilpmp.org/CDC/login.php>.

You may show your commitment to being a safe prescriber by using the following evidence-based interventions to lower overdose rates:

1. **Avoid co-prescribing** an opioid and a benzodiazepine. Opioids and benzodiazepines can have additive central nervous system depressant effects.
2. **Avoid opioid prescribing for chronic pain and avoid/minimize opioid prescribing for acute pain.** According to the Centers for Disease Control and Prevention (CDC), clinicians should avoid opioids for chronic pain, and when necessary for acute pain, start with the lowest effective dose of immediate-release opioids. Three days or less is often sufficient to address acute pain. Opioids should not be considered first-line

or routine therapy for chronic pain.

3. **Taper opioids to safer doses.** The CDC recommends that for patients already on long-term high-dose opioid therapy, taper to a dose that is lower than 50 morphine milligram equivalents (MME) and consider slow opioid tapers as well as pauses in the taper if needed for long-term users.
4. **Avoid “the 90-day cliff.”** One California study found that nearly 70% of patients who died of prescription-related overdoses were prescribed scheduled drugs for 3 consecutive months.¹ The CDC recommends opioids should be discontinued if benefits do not outweigh risks (if realistic goals for pain and function have not been met).
5. **The CDC recommends prescribing naloxone** to patients on higher than 50 MME of opioids per day.
6. **Prescribed medications for opioid use disorder.** Clinicians should offer medications for opioid use disorder, such as buprenorphine/naloxone, to their patients with opioid use disorder. Physicians, physician assistants, and advanced practice nurses can file a waiver to prescribe buprenorphine for the indication of opioid use disorder by visiting the SAMHSA website (<http://www.samhsa.gov/medication-assisted-treatment/become-buprenorphine-waivered-practitioner>) or by calling SAMHSA at [contact]. On April 28, 2021, SAMHSA announced that it will waive the training requirement for physicians, physician assistants, and advanced practice nurses to become waivered to prescribe buprenorphine for the indication of opioid use disorder. Further, you can use the Epic Social Determinants of Health (at the bottom left of your Storyboard), click on “Select Community Resources”, and find “Substance Use” resources.

When your next patient presents with pain, keep the above 6 recommendations close at hand to assist with their safe care. Also, be comfortable voicing your concern about prescribing safety with them so that they are also aware of the dangers associated with scheduled drugs. We also encourage you to routinely log into ILPMP and learn more about the prescriptions your patient received leading up to the death.

Again, this letter is meant to be informative only, is not affiliated with other initiatives, and there is no expectation of reply. We understand that learning of your patient’s death can be difficult. We hope that you will take this as an opportunity to join us in preventing future deaths from drug overdose.

Sincerely,

[Medical Director or other similar role]

¹ Lev, R., Petro, S., Lee, O., Lucas, J., Stuck, A., Vilke, G. M., & Castillo, E. M. (2016). A description of Medical Examiner prescription-related deaths and prescription drug monitoring program data. *The American journal of emergency medicine*, 34(3), 510–514. <https://doi.org/10.1016/j.ajem.2015.12.023>

